6.4 Withdrawal of Subjects and/or Discontinuation of Treatment

A subject should be withdrawn from the study for any of the following:

- 1) Withdrawal of subject consent
- 2) Subject is lost to follow-up
- 3) Investigator determines that withdrawal from the study is in the best interest of the subject.
- 4) Subject is non-compliant with protocol-mandated activities.
- 5) Occurrence of any intercurrent condition, injury, or disease that becomes apparent during the study and necessitates the termination of the subject from the study.
- 6) Administrative reason (e.g., termination of the clinical study by a regulatory agency or the sponsor)

A subject should be discontinued from treatment for any of the following:

- 1) Subject is not at least 75% compliant with study drug administration at any study visit ([Section 4.4.](#))
- 2) Occurrence of defined unacceptable toxicity ([Section 4.5](#))
- 3) Investigator determines that discontinuation of treatment is in the best interest of the subject.
- 4) Occurrence of any intercurrent condition, injury, or disease that becomes apparent during the study and necessitates the discontinuation of treatment.
- 5) Pregnancy
- 6) Subject requires use of prohibited concurrent medication
- 7) Subjects answering "yes" to Suicidal Ideation item 4 or 5 on the C-SSRS during the study must be withdrawn from the study treatment. Investigators should also withdraw subjects from treatment if, in the judgment of the investigator, the subject develops other indicators of significant risk of suicide. In the event that suicidal ideation is observed in any study subject, the investigator will manage the situation as he/she deems medically and psychiatrically appropriate.

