4.4 Study Drug Accountability and Compliance

Subjects will be instructed to return all used empty bottles and unused study drug at each visit.

The investigator or their appointed designee is responsible for ensuring that deliveries of study drug are correctly dispensed and recorded, that the product is handled and stored safely and properly, and that it is only being given to subjects in accordance with this protocol.

Sites will keep a current log of drug accountability recording:

- What drug supply was received from the sponsor
- What drug supply was dispensed to each subject
- What drug supply is current in inventory
- What drug supply was destroyed or returned to the sponsor for destruction

Note: Drug accountability is the responsibility of the investigator; a written account will be required for all discrepancies.

If the study drug supplies appear to be damaged/missing upon arrival at the investigational site, the sponsor should be contacted immediately.

the sponsor's designated monitor must verify all accountability records during periodic monitoring visits. Unused and used study drug must be stored on site until such accountability has taken place and authorization is received from the sponsor or sponsor's designee that the study drug may be returned or destroyed.

To stay in the study, subjects will be required to have taken at least 75% of their study treatment doses. A subject will be considered non-compliant if they have missed more than 25% of the required doses between visits. The minimum number of required doses per 7 days is detailed below:

- Week 1: 11/14 doses (22 capsules)
- Week 2: 11/14 doses (44 capsules)
- Week 3 to 4: 21/28 doses (105 capsules)

If compliance is less than 75% or greater than 125% at any visit, the reason(s) must be noted and the subject's continued participation in the study should be discussed with the study safety representative. Subjects should not make up for missed doses.

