6.4.1 Follow-up Procedures for Subjects Who Withdraw/Discontinue Prematurely

If a subject withdraws from the study, attempts should be made to contact the subject to determine the reason(s) for discontinuation. If a subject does not return to the clinic for follow-up visits, attempts should be made to contact the subject via phone, email, or mail. At least 3 documented attempts (one of which should be a certified letter) should be made to contact the subject before declaring a subject lost to follow-up. The study safety representative must be informed as soon as possible if a subject discontinues or withdraws early.

The date and the reason for study drug discontinuation or subject withdrawal from the study must be recorded on the Case Report Form. In case of early discontinuation or withdrawal of a subject, every effort must be made to report all study-mandated observations up to the time of discontinuation/withdrawal as completely as possible.

Subjects who are removed from treatment for AE(s) should be followed for resolution of the AE(s) (see [Section 10.2.3](#)) and should complete all assessments scheduled for the EOS Visit as well as all assessments that they are capable of completing on the Visit day if the decision to remove from treatment is made on a Visit day. Likewise, if the investigator plans to temporarily interrupt dosing because of an AE and the decision is made on a Visit day, then the subject should complete all scheduled assessments that they are capable of completing on the Visit day they appear.

If the reason for discontinuation/withdrawal is medical and the subject has not withdrawn consent, the subject should remain under the supervision of the investigator until the medical issue is resolved or otherwise declared stable.

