6.4.2 Procedures for Replacing Subjects Who Withdraw/Discontinue Prematurely

Subjects who withdraw from the study or discontinue treatment prematurely will not be replaced.

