11.4 Analysis Populations

The populations defined for analysis will include the intent-to-treat (ITT) population, safety population, and a pharmacokinetic population. Additional analysis populations may be defined to evaluate study results. Any additional analysis populations will be defined in the SAP.

- **Intent-To-Treat Population:** The ITT population will include all subjects who are randomized. The ITT population will be used for analyses of accountability, demographics, and efficacy. Subjects will be analyzed according to the treatment as randomized.
- **Safety Population:** The safety population will include all subjects who are randomized and receive at least one dose of randomized treatment. Subjects who receive treatment other than that intended will be analyzed according to the treatment received. The safety population will be the primary population for all analyses of safety data.
- **PK Population:** The PK population will consist of all subjects for whom PK samples were obtained, received study treatment, and for whom sufficient plasma concentrations are available.

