11.6 Missing, Unused and Spurious Data

Every effort will be made to obtain required data at each scheduled visit from all subjects who have been randomized. In situations where it is not possible to obtain all data, it may be necessary to impute missing data. Details of imputation methods will be presented in the SAP.

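### Section 6.4 removes randomised subjects from the study for non-compliance with protocol activities, against the data-collection aim in 11.6, and leaves avoidable, possibly informative gaps in the Day 28 endpoint

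*Protocol*

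**What the plan says.** All references are to the current protocol version, which plans approximately 106 subjects.

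- **Section 6.4** keeps two lists. The first opens "A subject should be withdrawn from the study for any of the following", and its item 4 reads "Subject is non-compliant with protocol-mandated activities". No threshold is given, no particular activities are named, and there is no exception for a subject still willing to attend. The second list covers discontinuation of treatment. Its first item is "Subject is not at least 75% compliant with study drug administration at any study visit".
- **Section 6.4.1** says that on early discontinuation or withdrawal "every effort must be made to report all study-mandated observations up to the time of discontinuation/withdrawal as completely as possible". Its further assessments apply to subjects removed from treatment, or interrupted, because of adverse events. Its continued supervision applies to medical reasons. Neither covers withdrawal under item 4.
- **Section 6.4.2** rules out replacement: "Subjects who withdraw from the study or discontinue treatment prematurely will not be replaced".
- **Section 11.6** states: "Every effort will be made to obtain required data at each scheduled visit from all subjects who have been randomized".
- **Section 11.4** defines the ITT population as everyone randomised, and adds: "The ITT population will be used for analyses of accountability, demographics, and efficacy".
- **Sections 3.3.1 and 8.1.1** make the primary endpoint the Day 28 change in TETRAS Performance, scored centrally from video.

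**The concern.** Stopping study drug and leaving the study are different events, and 6.4 treats them as such by keeping two lists. Item 4 is in the list that ends participation. With 6.4.1, it ends outcome collection for a randomised subject because of something that happened after randomisation, while 11.6 tells the same site to pursue every scheduled visit for that subject.

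Loss through withdrawn consent or loss of contact cannot be prevented. Loss that follows from a protocol rule can be. It may also be informative: a subject who feels unwell on drug, or who sees no effect, may become less compliant, and this can differ between arms. The subject stays in the ITT efficacy population but has no Day 28 value. The SAP can say how such a gap is handled, but it cannot recover a Day 28 video that was never recorded.

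**Working it through.** **1. The passages side by side.** Take a randomised subject who breaches a protocol procedure in week 2 but would still come to Visit 4.

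- Under 6.4 item 4, the subject should leave the study.
- Under 6.4.1, data are sought up to that point and not beyond.
- Under 11.6, data should be sought at every scheduled visit, including Day 28.
- Under 11.4, the subject counts in the efficacy analysis either way.

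The first two instructions and the third point in opposite directions for the same visit.

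**2. The plan's power figure.** Inputs from section 11.3: difference 5.5, SD 7.5, alpha 0.05 (two-sided per section 11), 53 per group, stated power at least 90%.

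Noncentrality = δ / (σ√(2/n)) = 5.5 / (7.5 × √(2/53)) = 5.5 / 1.457 = 3.775.

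- Normal approximation: Φ(3.775 − 1.960) = 96.5%.
- Two-sample t-test (noncentral t): 96.2%.
- With the rank-test adjustment (effective n = n × 3/π): 95.5%.

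The stated figure holds. For 90% power the t-test needs 41 per group, and 41 × π/3 = 42.9, so 43 with the non-parametric adjustment. Going from 43 to 53 leaves room for a loss of 1 − 43/53 = 18.9% per group. Section 11.3 says that 53 allows for dropouts and exclusions but gives no rate.

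**3. Power under loss.** The protocol gives no withdrawal rate, so the rates q here are assumptions, with n = 53(1 − q).

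| Loss per arm | n per group | Power, t-test | Power, rank-adjusted |
|---|---|---|---|
| 0% | 53 | 96.2% | 95.5% |
| 5% | 50.3 | 95.4% | 94.5% |
| 10% | 47.7 | 94.3% | 93.3% |
| 15% | 45.0 | 93.1% | about 92% |
| 18.9% | 43 | 91.9% | 90.7% |

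Power stays above 90% throughout.

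**4. Bias under an assumed scenario.** Let a share w of the active arm be withdrawn, and let these subjects differ by k points from the rest of the arm in what their Day 28 change would have been. A completers' mean for that arm is then off by w × k. With k = 5.5 (withdrawn active subjects would have had no benefit over placebo) and the placebo mean unaffected:

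- w = 5%: 0.05 × 5.5 = 0.28 points; an observed 5.5 stands for 5.2 in all randomised subjects.
- w = 10%: 0.55 points; 5.5 stands for 4.95.
- w = 15%: 0.83 points; 5.5 stands for 4.7.

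Varying both inputs, w from 5% to 20% and k from 3 to 8, gives a range of 0.15 (0.05 × 3) to 1.6 (0.20 × 8) points. A larger sample does not reduce this.

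**The case against.** Several points on the other side stand.

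- **The rule is not absolute.** The study-withdrawal list says *should*, whereas item 7 of the treatment list says *must*. Section 11.6 promises effort and accepts that some data cannot be obtained. Section 12.1.2 already has deviations documented with reasons, so not every lapse need trigger item 4. A reader might infer that sites are ordered to drop every non-compliant subject; the text does not go that far.
- **Section 11.4 does not require collection.** A reader might take it as a second source of that duty. It only defines who is analysed; the collection aim is in 11.6 alone.
- **The avoidable part may be small.** Low drug compliance and prohibited medication have their own entries in the treatment list, and loss to follow-up has its own study-withdrawal item. Some of what remains is missed visits, where the Day 28 video is lost whatever 6.4 says.
- **The bias figures are not evidence of harm.** They need an assumed rate, no benefit in every withdrawn active subject, an unaffected placebo arm and a completers' estimate. Section 11.6 leaves imputation to the SAP, so a completers' estimate cannot be presumed.
- **Removing the item has a side effect.** It also covers non-compliance with safety procedures, for which only the investigator-judgement reasons would remain.

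None of this justifies ending follow-up of a subject who would attend Day 28. It limits how strongly the point can be put.

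**Conclusion.** The concern holds as a conflict within the protocol. Section 6.4 item 4, read with 6.4.1, works against 11.6 and can create avoidable, possibly informative missing Day 28 outcomes in an efficacy population of all randomised subjects. The protocol fixes this rule badly; it is not a detail left to the SAP.

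A reader might infer that the trial is underpowered as a result. The figures do not support that: power is about 96% with 53 evaluable per group and about 93% at an assumed 15% loss, above the stated 90%. A reader might also infer that the treatment effect will be overstated by a known amount. That is not supported either: the size of any bias is unknown because no withdrawal rate is given, and the 0.3 to 0.8 points is an illustration under the assumptions set out above.

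The conflict over dosing compliance is separate. Section 4.4 says "To stay in the study, subjects will be required to have taken at least 75% of their study treatment doses", while 6.4 makes the same shortfall a reason to stop treatment. Those passages must also be reconciled, but this point does not rest on them.

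**What to change.** In section 6.4, remove item 4 from the study-withdrawal list, or keep it and state that it does not by itself end follow-up. Add that such non-compliance is recorded as a protocol deviation, which 12.1.2 already requires, and that the subject is asked to attend scheduled visits through the Day 28 TETRAS assessment unless another study-withdrawal reason in 6.4 applies (items 1, 2, 3, 5 or 6). Align 6.4.1 so that it no longer stops at the time of withdrawal for these subjects.

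Whether study drug continues stays with the separate treatment-discontinuation list, on which this point takes no position. The second option, keeping item 4 with a clarifying sentence, leaves a named entry for non-compliance with safety procedures.

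The cost is a short protocol amendment and a few more visits for subjects with imperfect adherence. Sample size, alpha and the primary analysis do not change.

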6.4.1 Follow-up Procedures for Subjects Who Withdraw/Discontinue Prematurely

If a subject withdraws from the study, attempts should be made to contact the subject to determine the reason(s) for discontinuation. If a subject does not return to the clinic for follow-up visits, attempts should be made to contact the subject via phone, email, or mail. At least 3 documented attempts (one of which should be a certified letter) should be made to contact the subject before declaring a subject lost to follow-up. The study safety representative must be informed as soon as possible if a subject discontinues or withdraws early.

The date and the reason for study drug discontinuation or subject withdrawal from the study must be recorded on the Case Report Form. In case of early discontinuation or withdrawal of a subject, every effort must be made to report all study-mandated observations up to the time of discontinuation/withdrawal as completely as possible.

Subjects who are removed from treatment for AE(s) should be followed for resolution of the AE(s) (see [Section 10.2.3](#)) and should complete all assessments scheduled for the EOS Visit as well as all assessments that they are capable of completing on the Visit day if the decision to remove from treatment is made on a Visit day. Likewise, if the investigator plans to temporarily interrupt dosing because of an AE and the decision is made on a Visit day, then the subject should complete all scheduled assessments that they are capable of completing on the Visit day they appear.

If the reason for discontinuation/withdrawal is medical and the subject has not withdrawn consent, the subject should remain under the supervision of the investigator until the medical issue is resolved or otherwise declared stable.

6.4.2 Procedures for Replacing Subjects Who Withdraw/Discontinue Prematurely

Subjects who withdraw from the study or discontinue treatment prematurely will not be replaced.

7 TREATMENT PLAN AND METHODS

7.1 Schedule of Assessments

The schedule of assessments is shown in [Table 3](#).

Table 3: Schedule of Assessments

Procedure	Visit	Screen	TREATMENT PERIOD				EOS
			Visit 1 Baseline	Visit 2	Visit 3	Visit 4	
	Study Day (window) End of week	-28 to 0	1	8 (± 2) 1	15 (± 2) 2	28 (-1) 4	35 (± 2) 5
1	Informed consent	X					
2	Demography/medical history	X					
3	Eligibility criteria	X					
4	Complete physical exam	X	X				X
5	Targeted physical exam			X			
6	Neurological exam	X	X	X	X		X
7	Vital Signs	X	X	X	X		X
8	Clinical laboratory tests	X	X	X	X		X
9	Electrocardiogram	X	X	X	X		X
10	Urine (+/- serum) pregnancy	X	X	X	X		X
11	Serum FSH	X					
12	TETRAS performance (video)	X	X	X	X		X
13	Accelerometry (Kinesia ONE)		X	X	X		X
14	TETRAS ADL	X		X	X		X
15	QUEST	X		X	X		X
16	CGI-S, CGI-I	X		X	X		X
17	PGIC			X	X		X
18	Goal Attainment Scale		X		X		X
19	Epworth Sleepiness Scale		X	X	X		X
20	C-SSRS	X	X	X	X		X
21	UM-PDHQ					As needed	
22	Pharmacokinetic sampling			X	X		X
23	Pharmacogenomic sampling		X				
24	Prior/Concomitant medications	X	X	X	X		X
25	AE review	X	X	X	X		X

Table 3: Schedule of Assessments - Continued

Procedure		Visit	TREATMENT PERIOD				EOS
Screen	Baseline		Visit 1	Visit 2	Visit 3	Visit 4	
Study Day (window)			1	8 (± 2)	15 (± 2)	28 (-1)	35 (± 2)
End of week	-28 to 0		-	1	2	4	5
26 Study drug administration in clinic							
27 Dosing			X	X	X	X	
28 Drug compliance				X	X	X	

ADL - activities of daily living; AE - adverse event; CGI-I - Clinical Global Impression - Improvement; CGI-S - Clinical Global Impression - Severity; C-SSRS - Columbia Suicide Severity Rating Scale; EOS - end of study; FSH - follicle stimulating hormone; FU - follow-up; PGIC - Patient Global Impression of Change; QUEST - Quality of Life in Essential Tremor Questionnaire; TETRAS - The Essential Tremor Rating Assessment Scale; UM-PDHQ - University of Miami Parkinson's Disease Hallucinations Questionnaire.

1. Informed consent must be signed prior to initiation of all other screening procedures (Section 12.2.3).
2. Conditions recorded in medical history will not be reported as adverse events unless the pre-existing condition worsens in severity or frequency. Medical history will include handedness, the age at onset of tremor and whether tremor is responsive to alcohol.
3. Subjects must meet all criteria specified in Sections 6.2 and 6.3. Eligibility will be confirmed by a central reviewer. Subjects taking primidone at screening who are deemed eligible for participation and are willing to discontinue primidone will be allowed an additional 2 weeks of screening (a total of 6 weeks/42 days) to ensure safe primidone discontinuation.
4. A complete physical exam will include height (screening only), weight, and examination of general appearance, skin, neck (including thyroid), eyes, ears, nose, throat, heart, lungs, abdomen, lymph nodes, and extremities. Genital, rectal, and breast examination may be excluded if not clinically indicated (Section 10.1.2). Complete physical examination need not be repeated at Visit 1 (Day 1) if Day 1 is \leq 7 days from the screening visit.
5. A targeted physical exam will be based on subject reports of signs and symptoms and investigator's observations (Section 10.1.2).
6. A neurological examination will include assessment of mental status (which should include assessment of orientation to person, place, time, and situation) and examination of cranial nerves II-XII, motor and sensory exam, reflexes, coordination, stance, gait and balance (Section 10.1.3). The details of the examination are left to the discretion of the investigator or the investigator's qualified designee but should be sufficiently comprehensive to enable a determination of whether the identified items are within the range of normal or are abnormal, and specific abnormalities should be described, e.g., "not oriented to time", or "left cranial nerve VII palsies", etc.
7. Vital signs include body temperature, systolic and diastolic blood pressure, pulse rate and respiration rate. Blood pressure and pulse rate will be measured in the recumbent position after at least 2 minutes of recumbency, and both measured again after approximately no less than 1 minute of standing. Subjects should be observed carefully for dizziness or unsteadiness while standing and allowed to sit if such occurs. Blood pressure and pulse rate should be recorded as soon as possible after sitting if the subject cannot stand for 1 full minute. At Screening, triplicate recordings of blood pressure and pulse rate will be made. The average of the 3 measurements will be used for comparison to single recordings at Visits 1 - 4. On Visits 1, 2, 3 & 4

(dosing days) orthostatic BP and pulse rate will be measured before dosing (recumbent and standing) and approximately 1-2 hours after dosing (recumbent and standing) as convenient between other required visit procedures. During any visit, blood pressure and pulse rate are to be assessed at any time subjects appear faint or complain of dizziness or other symptoms suggestive of hypotension. Respiratory rate and temperature will be measured in the recumbent position and need only be measured one time (with the first set of BP/pulse measurements). (Section 10.1.4.)

8. Clinical chemistry, hematology, urinalysis and coagulation panel. See Section 10.1.5 for complete details. Screening labs need not be repeated at Visit 1 (Day 1) if Day 1 is \leq 7 days from the screening visit. A positive drug screen will result in exclusion from the study unless it is explained by use of an allowed prescription medication (Section 10.1.6).
9. A triplicate 12-lead ECG will be performed at Screening and End of Study. At Visits 1, 2, 3 and 4 triplicate ECG will be performed predose and approximately 1-2 hours after the dose as convenient between other required visit procedures. All ECGs should be performed after at least 10 minutes of recumbency. (Section 10.1.8)
10. Women of childbearing potential only. A positive urine pregnancy test will be confirmed via serum testing. (Section 10.1.6)
11. Serum FSH only as needed to determine menopausal status in females < 62 years old with history of ≥ 12 months of amenorrhea without another cause.
12. Execution of the TETRAS Performance subscale will be video recorded for assessment by the central reader. Assessment by the site rater should be performed during the videotaping session. At Visit 1, the TETRAS Performance subscale should be performed prior to administration of study drug in the clinic. At Visits 3 and 4, the TETRAS Performance subscale should be performed during a window of 1 to 3 hours after administration of study drug in the clinic. (Section 8.1.1)
13. The Kinesia ONE device will be worn in the clinic after execution of the TETRAS Performance subscale assessment and, at Visit 1, prior to administration of study drug in the clinic. (Section 8.2.1)
14. TETRAS ADL: A 12 item scale where each item is rated on a 0 to 4 scale, with 0 representing normal activity and 4 representing severe abnormality. The sum of the individual scores provides the overall score, ranging from 0 to 48. At Visit 1, the TETRAS ADL subscale should be performed after the TETRAS Performance subscale (performed during a window of 1 to 3 hours after administration of study drug in the clinic) and Kinesia ONE accelerometry and prior to administration of study drug in the clinic. At Visits 3 and 4, the TETRAS ADL should be performed after the TETRAS Performance subscale and Kinesia ONE accelerometry. (Section 8.1.2)
15. QUEST: a 30-item quality of life questionnaire (Section 8.3.1)
16. The Clinical Global Impression Severity (CGI-S) will be administered at Visit 1. The Global Clinical Impression Improvement (CGI-I) will be administered at Visits 3 and 4. (Section 8.3.2)
17. The Patient Global Impression of Change (PGIC) will be administered at Visits 3 and 4. (Section 8.3.3)
18. Subjects will identify 3 specific, personal goals at Visit 1. Progress towards the goals will be assessed via Goal Attainment Scaling (GAS) at Visit 4. (Section 8.3.4)
19. The Epworth Sleepiness Scale is intended to measure daytime sleepiness. (Section 10.1.10)
20. C-SSRS identifies behaviors that may be indicative of an individual's intent to commit suicide. Subjects answering "yes" to Suicidal Ideation item 4 or 5 on the C-SSRS during the study must be withdrawn from the study treatment. (Section 10.1.9)
21. The UM-PDHQ is a 20-item clinician-administered questionnaire that quantitatively and qualitatively assesses hallucinations. The UM-PDHQ will be completed for any subject who reports hallucinations. (Section 10.1.11)

22. Collection of samples will occur pre-dose on Visits 2, 3, and 4. Additionally, at Visit 4, a post-dose sample will be collected as close to 4 hours post-dose as possible, but within the window of 4-6 hours post-dose (i.e., a total of two PK samples are collected at Visit 4. [\(Section 9.1\)](#))
23. A sample for pharmacogenomic testing will be collected in all subjects except where prohibited by local regulation. [\(Section 9.3\)](#)
24. Concomitant medications will be recorded from the time of informed consent through the End of Study. See [Section 7.3](#) for a list of prohibited and restricted medications. At each visit, the study site staff will re-confirm the dose and schedule of other anti-ET drugs the subject is taking.
25. AEs will be collected from signature of the ICF through 30 days after the last dose of study drug [\(Section 10.2.2\)](#). Adverse events will be followed for resolution in accordance with [Section 10.2.3](#).
26. The first dose of study drug at each dose level will be administered in the clinic. Subjects will be instructed to eat breakfast. At Visits 2, 3, and 4 subjects should hold their morning dose, as their dose will be administered in the clinic after the subject has undergone the first set of orthostatic VS and required pre-dose PK sampling, and/or has been evaluated by the investigator for suitability to undergo specified dose increase. Subjects will remain under observation for a minimum of 2 hours post dosing prior to discharge at Visits 1, 2 and 3, or the time that is required to complete all of the required procedures for the visit [\(Section 4.3\)](#).
27. Subjects will initiate dosing at 4 mg (2 capsules) administered twice daily with food. After 7 days dosing, the dose will be increased to 8 mg (4 capsules) twice daily, per subject tolerance. After 7 days at 8 mg BID, the dose will be increased to 10 mg (5 capsules) twice daily, per subject tolerance (Section 4.3.).
28. Compliance will be assessed via pill counts. [\(Section 4.4.\)](#)

